Effectiveness of an Occupation-Based Intervention Compared with Therapeutic Exercise for
Older Adults with Shoulder Osteoarthritis: A Pilot Randomized Controlled Trial

NCT Number: Not Assigned

Document Date: 10/04/2019

Statistical Analysis Plan (SAP)

Method

Research Design and Participants

We conducted a single-center, parallel-group RCT in an outpatient clinic. Participants were recruited via convenience sampling from the assisted and independent living facility where the outpatient clinic was located. Inclusion criteria were diagnosis of shoulder osteoarthritis and ages 65 years or older. Diagnosis was confirmed by physician examination or radiographic imaging. Exclusion criteria were previous shoulder injuries, acute pathology, previous shoulder surgery, current use of pain medication, inflammatory arthritis, upper extremity neuropathy or myopathy, current participation in a home exercise program, or a score of <18 on the Mini-Mental State Examination (MMSE).

This study was approved by the Bay Path University Institutional Review Board. All participants gave written informed consent to participate. Eighteen older adults were recruited for the study, four did not meet the MMSE criteria, and two did not have a confirmed diagnosis of shoulder osteoarthritis. Two participants withdrew from the study prior to randomization. Computer-based randomization was used to allocate the remaining ten participants into two groups: the Ten participants ($N = 10$) were randomly allocated to the OBI + TE ($n = 5$) or the TE ($n = 5$) group.

Outcomes Measures

The Quick Disabilities of the Arm, Shoulder and Hand (QuickDASH) (Beaton, Wright, Katz, Upper Extremity Collaborative Group, 2005) questionnaire was the primary outcome measure and was used to assess the impact of the intervention on physical function and symptoms of shoulder osteoarthritis. Scores range from 0 to 100. A lower score indicates less disability. The Canadian Occupational Performance Measure (COPM) was used to determine the

effect of the intervention on participants' self-perception of occupational performance and satisfaction over time (Law et al., 1990). Shoulder range of motion (ROM) was measured using a functional test established by Burner et al. (2014). Active abduction, flexion, external rotation, and internal rotation of the shoulder were assessed with participants seated on the edge of a mat with no back support and hips and knees at 90 degrees using a 3-point scale for ROM and pain (Burner et al., 2014). A Jamar hand dynamometer was used to measure the grip strength of the participants (che Daud et al., 2016). Pain was measured using the Numeric Pain Rating Scale (NPRS) (Hawker, Mian, Kendzerska, & French, 2011).

Procedure

Participants were randomly allocated using a computer-generated random number table. Outcome measures were administered prior to the intervention, a week after the conclusion of the intervention, and four weeks after the intervention ended. Protocols for occupation-based intervention for the treatment of upper extremity musculoskeletal disorders vary widely. According to a systematic review by Weinstock-Zlotnick & Mehta (2019), occupation-based interventions ranged from 2 to 10 weeks in duration, 1 to 5 sessions per week, with individual sessions lasting at least 30 minutes to a maximum of 3 hours. For this study, both groups were seen for 60-minute sessions, two times per week, for six weeks. The sessions for the OBI + TE group consisted of 30 minutes of TE followed by 30 minutes of OBI. The TE group sessions consisted of 60 minutes of TE. All participants received ten minutes of moist heat on the affected shoulder as a preparatory activity before the session started.

Control group. The TE protocol was completed systematically. Passive range of motion (PROM), active-assistive range of motion (AAROM), active range of motion (AROM), and

strengthening activities were completed sequentially. Participants were advised to respect and avoid pain with all exercises.

Intervention group. COPM results were used to select client-centered occupations, collecting and placing items in cabinets, washing windows and tables, and hanging clothes on a clothesline, for the OBI intervention. To make the activities more meaningful and relevant, interventions were completed within a simulated home environment. Participants were encouraged to use the affected upper extremity as much as possible, but to respect pain. The same TE protocol as the control group was completed prior to OBI, but with fewer repetitions, as a preparatory activity for the OBI.

Data Analysis

Data was collected and stored in a secure and locked file cabinet to protect the confidentiality of the participants. Statistical analyses were conducted using IBM SPSS Statistics (Version 23.0; IBM Corp., Armonk, NY). Descriptive statistics for all continuous variables included mean, standard deviation, and range. Descriptive statistics for categorical variables included frequencies and percentages. Paired sample t-tests were completed for each group for both the one week and four week follow up assessments to determine the effectiveness of the treatment protocol over time. Three sets of paired t-tests were used to compare the groups to each other at baseline, one week posttreatment, and four weeks posttreatment. The statistical significance level was set at $p < 0.05$ (two-tailed).

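### Scoring and analysis of the 3-point shoulder ratings are unspecified; if the only named test, the t-test, is applied to single items at n = 5, its p-value can be undefined or fall as benefit shrinks

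*Combined protocol and SAP*

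**What the plan says.** In Outcomes Measures, "Active abduction, flexion, external rotation, and internal rotation of the shoulder were assessed", "using a 3-point scale for ROM and pain". The section cites a published functional test for this but does not say how the categories are coded, whether ROM and pain are rated separately, or whether the four movements are combined. QuickDASH is named as the primary outcome, so these ratings are secondary.

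Research Design and Participants says that the ten participants "were randomly allocated to the OBI + TE ($n = 5$) or the TE ($n = 5$) group".

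Data Analysis has two sentences on inference. Within arms, "Paired sample t-tests were completed for each group for both the one week and four week follow up assessments". Between arms, "Three sets of paired t-tests were used to compare the groups to each other at baseline, one week posttreatment, and four weeks posttreatment". Significance is judged at 0.05, two-sided. No other test is named and no outcome is exempted.

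The same section splits the descriptive statistics by type of variable: "Descriptive statistics for all continuous variables included mean, standard deviation, and range", and "Descriptive statistics for categorical variables included frequencies and percentages". It does not list which outcomes fall in which class.

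**The concern.** A rating with three ordered categories, measured in five people, gives change scores with only a few possible values and many ties. The t-statistic divides by the standard deviation of those changes. When everyone changes equally, that standard deviation is zero and there is no test. When all but one change equally, it is small and the t-statistic is large. A weaker result can then be called significant while a better one gets no p-value.

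The natural reading of the plan leads there, because the t-test is the only inferential method and the outcome measures are collected at the time points that are tested. The plan has no ordinal or exact method and no rule for a test that cannot be computed. At stake is whether p-values reported for shoulder ROM and pain on movement can be interpreted.

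This is separate from the use of paired tests to compare two independent arms. Correcting the pairing would leave the problem in place.

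**Working it through.** The plan gives no p-value, power or sample-size figure for this outcome, so there is none to reproduce.

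**Inputs from the document:** three ordered categories and four movements (Outcomes Measures); five participants per arm (Research Design and Participants); paired t-tests at two-sided 0.05 (Data Analysis). **Assumptions:** categories coded as consecutive integers, one item tested at a time, all five participants assessed.

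**Within an arm.** For changes d in five participants, t = mean(d) / (SD(d)/√5) with 4 degrees of freedom. The exact comparison is the sign-flip test over the 2^5 = 32 sign patterns. When k participants improve by one category and the rest are unchanged, its two-sided p is 2/2^k.

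Worked case, four of five improve by one category: the mean is 0.8; the squared deviations sum to 4 × 0.04 + 0.64 = 0.80; the variance is 0.80/4 = 0.20; SD = 0.447; t = 0.8/(0.447/√5) = 4.00; p = 0.016. The exact p is 2/16 = 0.125.

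| Changes in the five participants | Mean | SD | t | t-test p | Exact p |
|---|---|---|---|---|---|
| 1,1,1,0,0 | 0.6 | 0.548 | 2.45 | 0.070 | 0.25 |
| 1,1,1,1,0 | 0.8 | 0.447 | 4.00 | 0.016 | 0.125 |
| 2,1,1,1,0 | 1.0 | 0.707 | 3.16 | 0.034 | 0.125 |
| 1,1,1,1,1 | 1.0 | 0 | undefined | none | 0.0625 |
| 2,1,1,1,1 | 1.2 | 0.447 | 6.00 | 0.004 | 0.0625 |
| 2,2,2,2,2 | 2.0 | 0 | undefined | none | 0.0625 |

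Moving from the second row to the fourth, one more participant improves and nobody does worse, yet the p-value goes from 0.016 to none. Moving from the second row to the third, one participant gains more and p rises from 0.016 to 0.034. The exact p never rises as benefit grows down the table.

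**Between arms, independent-groups t-test on change.** Four of five versus none improved by one category: the variances are 0.20 and 0; the pooled variance is 0.10; the standard error is √(0.10 × 2/5) = 0.20; t = 0.8/0.20 = 4.00 with 8 degrees of freedom; p = 0.004. The exact p is 2 × C(5,4)/C(10,4) = 10/210 = 0.048. Five of five versus none: both variances are zero, so t is undefined. The exact p is 2/C(10,5) = 2/252 = 0.0079.

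**Effect of summing.** If the four movements are summed, changes of 4,4,4,4,3 give t = 19.0 and p = 0.000045 against an exact p of 0.0625. Identical changes become less likely on the wider scale, but a within-arm t-test can still disagree sharply with exact inference.

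**False positives.** Suppose changes of −1, 0 and +1 with equal chances of moving up and down. The paired t-test at 0.05 then rejects with probability 0.0008, 0.0096, 0.032, 0.051 and 0 when 80%, 60%, 40%, 20% and 0% are unchanged. None is materially above 0.05.

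**How often the test is undefined (assumed scenarios).**
- 60% unchanged, 20% moving each way: 0.6^5 + 2 × 0.2^5 = 0.078.
- 80% unchanged, 10% moving each way: 0.8^5 + 2 × 0.1^5 = 0.328.
- 80% improving by one category, the rest unchanged: 0.8^5 + 0.2^5 = 0.328.

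In the first two, nearly all of the probability (0.6^5 = 0.0778 and 0.8^5 = 0.3277) is that nobody changed. Only in the third does undefined usually mean that everyone improved.

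**The case against.** The strongest objection is that nothing in the document says these ratings are t-tested. The t-test sentences name no outcome, and the provision for categorical variables leaves room for the ratings to have been only described. The cited test may also define a total, in which case the single-item examples do not arise. This stands: item-level t-testing is an inference. What remains is that the plan leaves both questions open and offers no other inferential method.

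Second, the between-arm example uses change from baseline, whereas the plan compares the arms at each visit. On visit scores, an independent-groups t-test is undefined only if ratings are identical within each arm at that visit. This also stands. The example shows that repairing the pairing does not by itself suit the t-test to this scale; it does not describe the planned analysis.

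Third, the exact within-arm floor of 2/32 = 0.0625 comes from having five participants. It applies equally to QuickDASH, grip strength and the pain scale. That is correct, and it is why the fix does not rely on within-arm tests.

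A reader might also infer several stronger things that the documents do not support:

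- *The best possible result gets no p-value because it is the best.* A one-category gain in all five is not the maximum on a 3-point scale, and the better pattern 2,1,1,1,1 gives p = 0.004. The trigger is identical change, whatever its size.
- *Any significant ROM result would be an artefact.* The rejection rates above do not show inflated error, and exact between-arm tests can also fall below 0.05.
- *The clearest response would be dropped from the report.* The plan does not say that an uncomputable test is omitted, and its descriptive statistics would still show the result.

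**Conclusion.** The concern holds in conditional form. The plan does not state how the 3-point ratings are scored, classed or analysed. If its only named test is applied to single items, p is undefined whenever all five changes are equal, and four of five improving gives 0.016 where exact inference gives 0.125. The fault is a p-value that is not monotone in benefit and that disagrees with exact inference. It is not a demonstrated excess of false positives.

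The figures assume integer coding, single-item scoring and complete data. How often an undefined test would occur cannot be derived from the document; the 8% to 33% range rests on assumed distributions and mostly reflects no change in anyone. The outcome is secondary in a ten-person pilot, so this is a worthwhile, inexpensive improvement and does not threaten the primary analysis.

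**What to change.** State in Data Analysis how the ratings are scored and which class of variable they belong to, and do not apply t-tests to single 3-point items. In their place:

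- Define a total ROM score and a total pain-on-movement score, using the instrument's own total if it has one and otherwise the sum of the four ratings.
- Compare the arms on change from baseline in each total, at each follow-up, with an exact permutation or exact rank-sum test. This returns a p-value for any data pattern and can reach 2/252 = 0.0079 with five per arm.
- Show every participant's values by arm.
- Report within-arm change and single movements descriptively, because an exact within-arm test at n = 5 cannot go below 0.0625.

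The cost is a few sentences in the SAP and no new data. Movement-specific and within-arm results lose their p-values. The section is written in the past tense, so any analysis already run must be repeated. If a total then has to be defined after data collection, the report should say so.

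### Neither the allocation of ten people nor the between-group tests make any described use of baseline QuickDASH, which leaves avoidable imprecision, though not bias

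*Combined protocol and SAP*

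**What the plan says.** Research Design and Participants reports that "Computer-based randomization was used to allocate the remaining ten participants into two groups" and that ten people "were randomly allocated to the OBI + TE ($n = 5$) or the TE ($n = 5$) group". Before that, "Two participants withdrew from the study prior to randomization". Procedure adds only that "Participants were randomly allocated using a computer-generated random number table". Blocking, stratification, matching and minimisation are not mentioned in either place.

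QuickDASH is the primary outcome under Outcomes Measures: "Scores range from 0 to 100. A lower score indicates less disability". On timing, Procedure says "Outcome measures were administered prior to the intervention, a week after the conclusion of the intervention, and four weeks after the intervention ended". It does not say whether the baseline assessment came before or after allocation.

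Data Analysis uses t-tests to "compare the groups to each other at baseline, one week posttreatment, and four weeks posttreatment". No model with the baseline score as a covariate is described. The documents give no power calculation, target effect, SD or baseline/follow-up correlation.

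**The concern.** With five people per arm, an allocation that ignores the baseline score leaves balance on the primary outcome to chance, and sizeable gaps are common. If follow-up means are then compared without reference to baseline, a share of that gap equal to the baseline/follow-up correlation carries into the follow-up difference. It can hide or imitate an effect in the means that readers will see.

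The information needed to reduce this noise is the baseline QuickDASH score, which the trial collects anyway. It can be used in the analysis, in the allocation, or in both. What is at stake is precision in a trial that has very little to spare.

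**Working it through.** **Inputs.** From the documents: 5 per arm (Research Design and Participants) and two-sided 0.05 (Data Analysis). Assumed, because the documents give no values: approximately normal scores, equal SD at baseline and follow-up, correlation ρ of 0.3 to 0.7, and effects of 0.5 to 1.5 SD. All results are in SD units. The unadjusted comparator is an independent-samples t-test. The plan states no imbalance or power figure to reproduce; its participant flow is consistent (18 − 4 − 2 − 2 = 10 = 5 + 5).

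**1. Chance baseline gap under 5:5 allocation.** The SD of the difference in baseline means is √(1/5 + 1/5) = 0.632.
- Gap over 0.5 SD: 0.5/0.632 = 0.79, so 2(1 − Φ(0.79)) = 42.9%.
- Gap over 1 SD: 1/0.632 = 1.58, which gives 11.4%.
- Measuring the gap against the ten participants' own SD, averaged over the 252 possible splits, gives about 46% for normal scores, 45% for uniform and 48% for skewed. Coin-toss allocation without fixed arm sizes gives 45%.

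**2. Error rate of an unadjusted comparison.** In simulation, type I error over all allocations is 5%. Among allocations with a gap over 0.5 SD it is about 7% at ρ = 0.5 and 9% at ρ = 0.7; where the gap is smaller it is below 5%.

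**3. Adding the covariate under simple allocation.** The unadjusted difference has variance 0.40. The adjusted one has expected variance 0.4(1 − ρ²)(1 + 1/6). The 1/6 is the average price of estimating the slope when the arms differ by chance (8 within-arm degrees of freedom, less 2). Power is for a 1.5 SD effect.

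| ρ | Adjusted variance | Power, unadjusted | Power, adjusted |
|---|---|---|---|
| 0.3 | 0.4 × 0.91 × 7/6 = 0.425 | 55% | 52% |
| 0.5 | 0.4 × 0.75 × 7/6 = 0.350 | 55% | 60% |
| 0.7 | 0.4 × 0.51 × 7/6 = 0.238 | 55% | 76% |

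Variance breaks even where (1 − ρ²) × 7/6 = 1, so ρ = √(1/7) = 0.38. The lost degree of freedom (8 to 7) puts the break-even for interval width slightly higher.

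**4. Adding paired allocation to the covariate.** In simulations that rank the ten on baseline, form five consecutive pairs and randomise within each, the SD of the gap is 0.24. The chance of a gap over 0.5 SD is about 4%, and over 1 SD under 0.1%. Adjusted variance falls from 0.350 to 0.303 at ρ = 0.5 and from 0.237 (simulated) to 0.207 at ρ = 0.7, about 13% each. Mean interval width falls about 6%. Pairing removes nearly all of the 1/6 penalty: 0.303/(0.4 × 0.75) = 1.01. The same factor at ρ = 0.3 gives 0.4 × 0.91 × 1.01 = 0.37, below the unadjusted 0.40. Power of the adjusted analysis, simple to paired allocation:

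| Effect | ρ = 0.5 | ρ = 0.7 |
|---|---|---|
| 0.5 SD | 11.6% to 12.4% | 14.8% to 15.8% |
| 0.8 SD | 22% to 24% | 31% to 33% |
| 1.0 SD | 32% to 35% | 44% to 47% |
| 1.5 SD | 60% to 65% | 76% to 80% |

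Type I error stays at 5%.

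**5. Pairing without the covariate.** An independent-samples t-test still counts the baseline variation that pairing has taken out of the difference. Its type I error drops to about 3% (ρ = 0.5) or 1% (ρ = 0.7). Power at 0.8 SD drops from 20% to 17% or 14%.

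**The case against.** The strongest reply is that nothing is broken. Simple randomisation is valid, its chance imbalance is already in the standard error, and the 0.5 SD threshold is a reviewer's choice. That stands: a reader might infer from the 43% that the comparison is biased, and step 2 shows that over all allocations it is not. The contrast of 43% with 4% also flatters pairing. Once the covariate is in the model, pairing adds only a few points of power in a self-described pilot.

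Three further inferences go beyond the text.

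- **That no restriction of any kind was used.** The documents are silent. An unrestricted table yields exactly 5:5 in only 252/1024 = 24.6% of cases, so arm size may have been fixed. That would not balance QuickDASH, and the 43% already assumes 5:5. Nor does the use of paired t-tests between groups show that pairs were formed at allocation; no matching is described.
- **That all ten baseline scores were available at allocation.** The account of the remaining ten suggests that the people had been identified. It does not place their scores before randomisation.
- **That living level should also be balanced.** Recruitment was "from the assisted and independent living facility where the outpatient clinic was located", but the documents do not show that each participant's level was recorded or how many were in each. That element is not supported.

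Finally, the text is in the past tense. If allocation is complete, it cannot be changed, and rewriting the allocation sentence would misdescribe what was done. The analysis remedy is unaffected.

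**Conclusion.** The point holds as a modest, avoidable loss of precision, and not as the correction of a bias. The 43% rests on normal scores and a 5:5 split and is stable at 43% to 48% under the variants tried.

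Most of the recoverable precision lies in the analysis. How much depends on a correlation that the documents do not give: substantial at 0.7, small at 0.5, slightly negative at 0.3 under simple allocation. Balanced allocation adds about 6% in interval width on top, and is worth having only together with the covariate. The power figures for a 1.5 SD effect are illustrations, since the documents name no target effect.

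**What to change.** 1. **Analysis, whatever allocation was used.** In Data Analysis, compare the arms on QuickDASH at each follow-up with a linear model containing arm and baseline QuickDASH, and report the adjusted difference with its 95% confidence interval. Make this choice without reference to the observed baseline gap. It costs one residual degree of freedom and a small loss of power if the correlation is low; the data are already collected.
2. **Reporting.** State how the sequence was generated, how the 5:5 split arose, whether anything was balanced, and whether baseline was taken before or after allocation. This costs a sentence or two.
3. **Allocation, only if still open, or in the trial that follows this pilot.** Take baseline first, rank participants on QuickDASH, form five consecutive pairs, and let computer-generated random numbers choose the arm within every pair in a single step from coded identifiers. If enrolment is staggered, minimise on baseline QuickDASH with a random element. Two strata split at the median are a poor substitute: the chance of a gap over 0.5 SD falls only to about 32%.

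Item 3 costs a protocol sentence, a short script and a wait for baseline scores. It must not be adopted without item 1, because pairing followed by an unadjusted independent-samples t-test is conservative and loses power for moderate effects.

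### The SAP ties effectiveness only to within-arm paired t-tests, which do not estimate OBI + TE versus TE, and never says that the listed between-group tests decide

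*Combined protocol and SAP*

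**What the plan says.** The title asks about the effectiveness of an occupation-based intervention compared with therapeutic exercise. Research Design and Participants describes a parallel-group RCT with 10 participants, 5 per arm. Under Outcomes Measures, the QuickDASH "questionnaire was the primary outcome measure"; lower scores mean less disability. Neither a primary time point nor a primary contrast is named.

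Data Analysis has two sentences on testing:

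- Within arms: "Paired sample t-tests were completed for each group for both the one week and four week follow up assessments". The same sentence goes on to give the purpose of these tests: "follow up assessments to determine the effectiveness of the treatment protocol over time".
- Between arms: "Three sets of paired t-tests were used to compare the groups to each other at baseline, one week posttreatment, and four weeks posttreatment". No purpose is given beyond comparing the groups.

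The significance level is 0.05, two-tailed.

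The content of the arms is set out under Procedure. For the control arm: "The TE group sessions consisted of 60 minutes of TE". For the other: "The sessions for the OBI + TE group consisted of 30 minutes of TE followed by 30 minutes of OBI". The Intervention group paragraph adds: "The same TE protocol as the control group was completed prior to OBI, but with fewer repetitions". Both arms had heat beforehand: "All participants received ten minutes of moist heat on the affected shoulder".

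**The concern.** Randomisation protects the difference between the arms. It does not protect the change within one arm, which mixes any treatment effect with natural course, regression to the mean, and everything the arms share (TE, moist heat, session time). A paired t-test in the OBI + TE arm therefore answers a different question from the one in the title.

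The design makes this sharper, because OBI is substituted for TE and not added to it. Improvement in the OBI + TE arm is compatible with OBI + TE being better than, equal to or worse than a full hour of TE.

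As the SAP stands, a significant before-after change in the OBI + TE arm can be reported as effectiveness even if replacing half of the TE made no net difference or did harm. Which contrast decides determines what the trial can conclude about its own title question.

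**Working it through.** **Reading the text.** In Data Analysis, effectiveness appears once and is attached to the within-arm tests. The between-group sentence follows, with no statement that it is primary or decisive. No other section gives a rule for concluding effectiveness. The documents contain no power calculation, SD or expected change, so there is no stated figure to reproduce. The calculations below only show how large the consequence can be.

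**Inputs.** From the documents: 5 per arm, two-sided 0.05. Assumed: the standardised within-arm change dz (mean change divided by the SD of change), shown as a range, with normal data and one follow-up.

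**1. Equal true change in both arms, so OBI + TE has no advantage.** The paired test has 4 df and critical t = 2.776. The chance of significant improvement in one arm is P(T > 2.776), where T is noncentral t with 4 df and noncentrality dz × √5.

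| dz | dz × √5 | Significant improvement, OBI + TE arm |
|---|---|---|
| 0 | 0 | 2.5% |
| 0.5 | 1.118 | 14% |
| 1.0 | 2.236 | 40% |
| 1.5 | 3.354 | 71% |
| 2.0 | 4.472 | 91% |

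Above dz = 0 these are correct detections of change. They are false only if read as an advantage over TE. In simulation (200,000 trials per setting, dz 0.5 to 2.0, baseline to follow-up correlation 0.3, 0.5 and 0.7), an independent t-test at follow-up, a t-test on change and ANCOVA were each significant in 4.9% to 5.1% of trials.

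**2. OBI + TE truly worse, by 0.5 SD of change.** With dz 1.0 in OBI + TE against 1.5 in TE, the OBI + TE arm still shows significant improvement in 40% of trials; with 1.5 against 2.0, in 71%. The between-group t-test on change has 8 df, critical t = 2.306 and noncentrality −0.5 × √(5/2) = −0.79. It favours OBI + TE in 0.38% of trials and TE in 10.4%.

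**3. One arm significant and the other not.** The SAP does not state this as a rule, so it is only an illustration. With equal true change and p the within-arm rejection probability, exactly one arm is significant with probability 2p(1 − p). At dz 1.0, p = 0.401, which gives 2 × 0.401 × 0.599 = 48%. Over dz 0.5 to 1.5 the figure runs from 24% to 50%.

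**4. Precision of the between-group contrast with 5 per arm.**

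- Unadjusted 95% half-width: 2.306 × √(2/5) = 1.46 SD.
- ANCOVA: 2.365 × √((1 − r²) × 2/5 × 7/6), where r is the baseline to follow-up correlation and 7/6 allows for chance baseline imbalance. This gives 1.62 SD at r = 0, 1.40 at r = 0.5 and 1.15 at r = 0.7. It equals the unadjusted width at r = 0.43.
- The unadjusted test reaches 80% power at a true difference of about 2.02 SD; at 1 SD its power is about 29%.

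**The case against.** The strongest reply is that the comparison is already planned. The sentence after the within-arm tests compares the groups at all three time points. Given the title and the design, a reader could take the first sentence as describing change in each arm and the second as answering the trial question. The effectiveness phrase speaks of change over time and covers the TE arm equally, so it does not itself claim that OBI + TE is superior. The SAP states no rule that a within-arm result establishes superiority. Its own output would also show the TE arm: with equal true change, both arms improve significantly in about 16% of trials at dz 1.0 (0.401²) and 51% at 1.5 (0.711²). Finally, this is a pilot of 10 people, and the right contrast will not settle the question either.

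Much of this stands. Between-group tests are not absent, the milder reading is possible, every dz is assumed, and the percentages in steps 1 and 2 become errors only under the wrong reading. What does not follow is that the plan is adequate. Listing a test does not make it decisive, and the only analysis given an effectiveness purpose is the one that cannot answer the title question. Even on the milder reading, nothing prevents a within-arm result from being reported as effectiveness. The pilot label limits how firm a conclusion can be; it does not change which contrast the conclusion should rest on.

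The SAP also calls the between-group tests paired although the arms hold different people. That is a separate defect and is not counted here.

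**Conclusion.** The concern holds and should be fixed before any effectiveness conclusion is drawn. It rests on the wording of the SAP: effectiveness is assigned to within-arm tests, those tests do not estimate OBI + TE versus TE, and no section makes the between-group tests decisive. It does not depend on the arithmetic.

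The possible size is large. If within-arm changes lie between 0.5 and 1.5 SD of change, the stated effectiveness analysis is positive for OBI + TE in 14% to 71% of trials in which OBI + TE has no advantage, against about 5% for a valid between-group test. It stays positive in 40% to 71% of trials in which OBI + TE is worse by 0.5 SD of change (dz 1.0 and 1.5 in that arm). These figures assume normal data, the dz values shown and a single follow-up.

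**What to change.** Add to Data Analysis:

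> The effectiveness question is answered by the between-group difference in QuickDASH (OBI + TE minus TE) at [one named follow-up], from a method for independent groups, with a 95% CI. The other follow-up is secondary. Within-group tests are descriptive. A significant change in one group and not in the other is not evidence of a difference between treatments.

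The choice of follow-up, and the reason for it, must not depend on the results. The method can be an independent-samples t-test or, preferably if the baseline to follow-up correlation is expected to exceed about 0.43, ANCOVA with baseline QuickDASH. The document is in the past tense, so if results are already known the re-analysis should be labelled post hoc. It should be reported as a pilot estimate.

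The cost is a few sentences and a re-analysis of data already collected. Within-group improvement is lost as an efficacy claim. The interval will be wide (step 4 of the working), so a non-significant result would not show that the treatments are equal, and the report should say so.

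### The comparison of the two randomised groups is specified as a paired t-test, although the groups are independent and nothing links their members

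*Combined protocol and SAP*

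**What the plan says.** Research Design and Participants describes the design: "We conducted a single-center, parallel-group RCT in an outpatient clinic". The ten participants "were randomly allocated to the OBI + TE ($n = 5$) or the TE ($n = 5$) group". The Procedure section adds: "Participants were randomly allocated using a computer-generated random number table". Matched pairs, crossover and pair-wise randomisation are not mentioned anywhere.

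The Data Analysis section then uses paired tests for two different purposes. The first is change over time within each arm: "Paired sample t-tests were completed for each group for both the one week and four week follow up assessments". The second is the comparison between arms: "Three sets of paired t-tests were used to compare the groups to each other at baseline, one week posttreatment, and four weeks posttreatment". The significance level is 0.05, two-sided. No independent-samples test, analysis of covariance or mixed model is named.

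**The concern.** A paired t-test analyses differences within linked units. Linkage exists for the within-arm tests, where each person is measured before and after treatment. It does not exist between arms, because no OBI + TE participant corresponds to any particular TE participant. A paired procedure subtracts one column from another row by row, so the order in which people happen to be listed supplies the pairing. Re-sorting one arm's rows changes the answer. Because the arms are equal in size, the procedure would run without an obvious warning.

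These tests are the plan's only comparison of the randomised groups, and so its only direct answer to the question in the trial's title. The two follow-up comparisons on QuickDASH, the primary outcome, are the ones that matter most. With ten participants in total, giving up half the degrees of freedom is a material loss.

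**Working it through.** The plan gives no power calculation, standard deviation or target difference, so there is no stated figure to reproduce. From the documents: n = 5 per arm and two-sided alpha = 0.05. Assumed: normal data, equal variances, no correlation between arbitrarily paired people, and true differences d of 1, 1.5 and 2 SD.

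**Degrees of freedom and critical value**

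- Paired: n − 1 = 4, critical t = 2.776.
- Independent groups (pooled): 2n − 2 = 8, critical t = 2.306.
- Ratio: 2.776 / 2.306 = 1.20, so the threshold is 20% higher.

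**Power** (noncentral t, noncentrality d / √(2/5) = 1.581 d)

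| Assumed difference | Noncentrality | Independent, 8 df | Paired, 4 df |
|---|---|---|---|
| 1 SD | 1.581 | 28.6% | 23.1% |
| 1.5 SD | 2.372 | 54.9% | 44.0% |
| 2 SD | 3.162 | 79.1% | 66.3% |

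The difference detectable with 80% power is 2.02 SD for the independent test and 2.38 SD for the paired test.

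**Mean 95% CI half-width**, in SD units. This is critical t × E(s)/σ × √(2/5), with E(s)/σ = √(2/ν) Γ((ν+1)/2) / Γ(ν/2), where ν is the degrees of freedom.

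- Independent: 2.306 × 0.969 × 0.632 = 1.41.
- Paired: 2.776 × 0.940 × 0.632 = 1.65.

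**Dependence on row order.** The variance of the paired differences is s₁² + s₂² − 2 × (covariance across the chosen pairs). Only the covariance depends on the pairing, and there are 5! = 120 pairings. Take invented scores of 20, 28, 35, 41, 52 in one arm and 34, 40, 49, 58, 66 in the other. The mean difference is 49.4 − 35.2 = 14.2 under every pairing.

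- Both arms in ascending order: differences 14, 12, 14, 17, 14; SE = √(3.2/5) = 0.80; t = 17.75; p = 0.00006.
- One ascending, the other descending: differences 46, 30, 14, −1, −18; SE = √(632.2/5) = 11.24; t = 1.26; p = 0.275.
- Independent test: pooled variance (598.8 + 675.2)/8 = 159.25; SE = √(159.25 × 2/5) = 7.98; t = 1.78; p = 0.113, whatever the order.

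Of the 120 pairings, 15% (18) give p < 0.05.

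In simulated normal datasets, at least one pairing disagreed with the others on significance in about 30% of datasets with no true difference, about 60% at 1 SD and about 67% at 1.5 SD. This measures how often the verdict could be changed by choice of order. Two pairings drawn at random disagree less often: about 5.6%, 16% and 21% respectively.

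**Type I error.** With row order unrelated to outcome, simulated type I error was 4.95% paired and 4.93% independent. If each arm were sorted by score, it would be about 31%.

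**The case against.** The strongest reply is that the wording may be a slip. The preceding sentence correctly uses a paired test, and the word may have carried over when an independent-samples test was meant and run. The document contains no results or degrees of freedom that would settle this. That point stands: the text establishes that the wrong test is named, not that it was run, so the numerical consequences are conditional on a literal reading. It does not remove the need for correction.

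A second reply is that the paired test is not biased if rows were ordered without regard to outcome, for example by enrolment number. That is also right under the normal assumptions used here. What remains is lower power, a wider interval and a p-value that rests on a listing order the plan does not specify.

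Third, the 30% and 60% figures count any disagreement among 120 pairings. The random-pair rates are the better guide to an order nobody chose. The 31% type I error is an extreme case, and nothing in the documents suggests that rows were sorted by score.

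Fourth, a Welch test has at most 8 degrees of freedom, so the gain from moving to it is slightly smaller than the pooled figures show. It still has about 53% power at 1.5 SD, against 44% for the arbitrary pairing.

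Finally, loss of further participants through pairing is hypothetical. The two reported withdrawals came before randomisation. If one follow-up were missing, the paired test would keep four pairs (3 df) and drop a complete participant from the other arm, whereas an independent test would keep nine people (5 + 4 − 2 = 7 df).

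**Conclusion.** The concern holds. As written, the plan applies a paired test to two independent randomised groups, which conflicts with its own description of the design. The loss of degrees of freedom (8 to 4) and the higher critical value follow directly from five per arm and a two-sided 5% level. The power losses, about 11 percentage points at 1.5 SD (54.9 − 44.0) and 13 at 2 SD (79.1 − 66.3), rest on assumed effect sizes, normality and equal variances. The dependence of the p-value and interval on row order needs none of those assumptions. This should be corrected before any between-group result is relied on, because the plan contains no other comparison of the arms.

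**What to change.** Replace the sentence on comparing the groups with an independent-groups analysis at each follow-up. The minimum is a Welch independent-samples t-test. A baseline-adjusted comparison is preferable: regress the follow-up score on treatment group and baseline score, which leaves 10 − 3 = 7 residual degrees of freedom. Report the between-group mean difference with its 95% CI for each outcome at one week and four weeks, with QuickDASH first as the primary outcome. Keep paired tests for within-arm change only.

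Check the existing output. If the between-group results carry 4 degrees of freedom, or otherwise came from the paired procedure, re-run and replace them. If an independent test was in fact used, correct the wording and say so. The cost is one sentence of SAP text and at most a re-run in the same software, with no new data.
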